10.3.4. Safety Analyses

Safety measures will include AEs, hypoglycemia, unplanned infusion set changes and reasons, vital signs and weight, treatment exposure, laboratory measures, and antibodies to insulin lispro.

Events that are newly reported after the first dose of IP or reported to worsen in severity from baseline will be considered TEAEs. The Medical Dictionary for Regulatory Activities (MedDRA) lowest level term (LLT) will be used in the treatment-emergent assessment. The maximum severity for each LLT during the baseline period will be used as baseline severity.

SAEs, AEs reported as reason for discontinuation from the IP or study, and TEAEs will be summarized in tables using the MedDRA PT, sorted by decreasing frequency within the LY900014 treatment group. TEAEs will also be summarized by PT sorted by decreasing frequency within SOC for all TEAEs and by maximum severity. For events that are specific to only one sex, the denominator and computation of the percentage will include only patients from the given sex. The number and proportion of patients with at least 1 event for each type of event will be summarized and compared between treatment groups using Fisher's exact test. Serious adverse events, AEs reported as reason for discontinuation from the study, and TEAEs will be summarized for open-label Humalog during the lead-in period.

Hypoglycemia rates will be summarized for periods of 1 year and 100 years (severe hypoglycemia only). The rate of severe hypoglycemia per 100 years will be compared between treatment groups using the empirical method (details will be described in the SAP). For each of other categories of hypoglycemia, the number of hypoglycemia events during a specific period (rate) after randomization (for example, 0 to 4 weeks of treatment period) will be analyzed by using a negative binomial regression model including treatment. An offset defined as the log transformation of treatment exposure in the specific period (days)/365.25 days will be included in the model to estimate the rate of hypoglycemia per year. The proportion of patients with at least 1 hypoglycemic event in each category (incidence) during a specific period after randomization will be analyzed using a logistic regression model including treatment.

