6.2. Adjustments for Covariates

Stratification factors of this study include country, HbA1c stratum ($\leq 7.5\%$, $> 7.5\%$), and patient's personal CGM or FGM use during the study. Stratification factors will be entered into the IWRS for randomization and also collected in the database by electronic case report form (eCRF) or central laboratory. The analysis models will use the stratification factors as collected at randomization in the database as fixed effects.

For the primary analysis of HbA1c, the stratification factor of HbA1c stratum will not be included. Instead, the continuous value of baseline (Visit 4) HbA1c will be included in the analysis models.

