6.5. Multiple Comparisons/Multiplicity

A graphical approach for multiple comparisons (Bretz et al. 2011) will be used to strongly control the overall Type I error (2-sided alpha level of 0.05) for testing the treatment effect for the primary and multiplicity adjusted objectives listed in Section 4. See Section 6.11.2 for the details of graphical testing scheme.

No multiplicity test adjustment will be made for other objectives.

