6.12.3. Hypoglycemic Events and Other Adverse Events

6.12.3.1. Hypoglycemic Events

Hypoglycemia events that occur during the study will be captured using a paper diary starting from Visit 2 through Visit 801. Whenever hypoglycemia is suspected ($BG \leq 70 \text{ mg/dL}$ [3.9 mmol/L]), the patient should record the BG value, any associated symptoms, and the treatment administered. A set of events is counted as 1 event in analysis if the duration between adjacent events is ≤ 30 minutes.

The event with the highest severity will be selected for analysis with severity determined in the order of: 1) it is a severe hypoglycemia, 2) it has symptoms of hypoglycemia reported, and 3) it has the lowest blood glucose value. If there are multiple events tied in all 3 aspects, the event with the largest number of non-missing responses to the questions of nocturnal hypoglycemia and postmeal time frame will be selected. Hypoglycemia rates will be summarized for periods of 1 year and 100 years (severe hypoglycemia only). The rate of severe hypoglycemia per 100 years will be compared between treatment groups using the empirical method (see [Appendix 1](#) for details). For each of other categories of hypoglycemia, the number of hypoglycemia events during 0 to 16 weeks (rate) after randomization will be analyzed by using a negative binomial regression model including treatment. An offset defined as the log transformation of treatment exposure in the specific period (days)/365.25 days will be included in the model to estimate the rate of hypoglycemia per year. The proportion of patients with at least 1 hypoglycemic event in each category (incidence) during 0 to 16 weeks after randomization will be analyzed using a logistic regression model including treatment.

The following types of hypoglycemia events will be derived in the analysis data sets: documented hypoglycemia, severe hypoglycemia, nocturnal hypoglycemia, and non-nocturnal (daytime) hypoglycemia. Only severe hypoglycemia will be collected as AEs and all episodes of severe hypoglycemia will be considered as SAEs. Documented hypoglycemia will be based on $BG \leq 70 \text{ mg/dL}$ and $BG < 54 \text{ mg/dL}$.

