[Table ITRO 6.3](#) provides detailed statistical methods for each endpoint related to hypoglycemia. For these analyses, hypoglycemia events prior to the discontinuation (i.e., last dose) of IP will be summarized. Additional analyses for other types of hypoglycemic events not mentioned in the table may be conducted as needed.

A listing of patients with at least 1 severe hypoglycemia reported (as SAE) after randomization (including Visit 801) will be provided.

A list of MedDRA PTs will be used for the narrow search of potential severe hypoglycemia in spontaneously reported AEs. The events identified through the search strategy that are also reported as SAEs will be summarized and compared between treatments. Fisher's exact test will be used to assess the treatment difference in the proportion of patients with potential severe hypoglycemia.

Table ITRO 6.3. Summary of Analyses for Endpoints Related to Hypoglycemia

Endpoint	Analysis Period ^b	Statistical Method
Rate of hypoglycemic events (per patient per year) 
 • All Documented^a • Nocturnal^a • Non-Nocturnal (or Daytime) (Documented and between waking and bedtime)^a 	0-16 weeks	Negative binomial regression with treatment and log (exposure/365.25 days) as the offset in the model.
Incidence of hypoglycemic events 
 • All Documented^a • Nocturnal^a • Non-Nocturnal (or Daytime) (Documented and between waking and bedtime)^a 	0-16 weeks	Logistic regression with treatment
Rate of post-meal hypoglycemic events (per patient per year) 
 • All Documented^a 	$\leq 1, \leq 2, \leq 4$, and >2 to ≤ 4 , and >4 hours after start of a meal within 0-16 weeks	Negative binomial regression with treatment and log (exposure/365.25 days) as the offset in the model.
Incidence of post-meal hypoglycemic events 
 • All Documented^a 	$\leq 1, \leq 2, \leq 4$, and >2 to ≤ 4 , and >4 hours after start of a meal within 0-16 weeks	Logistic regression with treatment
Rate of severe hypoglycemic events (per patient per 100 years)	0-16 weeks	Exposure adjusted rate per 100 years (calculated by total number of events divided by total exposure for individual patients) will be provided and the empirical method (see Appendix 1 for details) will be used for treatment comparison.

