6.12.5. Vital Signs and Other Physical Findings

Post-baseline measurements and change from baseline to post-baseline for vital signs and physical characteristics (systolic blood pressure [SBP], diastolic blood pressure [DBP], pulse rate, weight, BMI) at the scheduled visits will be summarized for patients who have both baseline and at least 1 post-baseline result.

The measurements during the treatment period (0 to 16 weeks) will be analyzed by an MMRM model with treatment, baseline value of the response variable, visit, and visit by treatment interaction as fixed factors and patient as the random factor.

An ANCOVA model will also be used for the analysis of the last nonmissing observation (including early discontinuation visit) during the treatment period and during the entire study (up to Visit 801). The ANCOVA models are the same as those used for clinical laboratory measures.

The percentages of patients with treatment-emergent high or low vital signs and weight at any time during the treatment period (0 to 16 weeks) or during the entire study including safety

follow-up period will be summarized by treatment group for patients who have both baseline and at least 1 postbaseline measurement. A treatment-emergent high result is defined as a change from a value less than or equal to the high limit at all baseline visits to a value greater than the high limit at any time that meets the specified change criteria during the treatment period or during the entire study including safety follow-up period. A treatment-emergent low result is defined as a change from a value greater than or equal to the low limit at all baseline visits to a value less than the low limit at any time that meets the specified change criteria during the treatment period or during the entire study including safety follow-up period. Treatment comparison will be based on Fisher's exact test. [Table ITRO 6.4](#) will be used to define the low and high limits and change thresholds.

Table ITRO 6.4. Categorical Criteria for Abnormal Treatment-Emergent Blood Pressure and Pulse Measurement, and Categorical Criteria for Weight for Adults

Parameter	Low	High
Systolic BP (mm Hg) (Supine or sitting – forearm at heart level)	≤ 90 and decrease from baseline ≥ 20	≥ 140 and increase from baseline ≥ 20
Diastolic BP (mm Hg) (Supine or sitting – forearm at heart level)	≤ 50 and decrease from baseline ≥ 10	≥ 90 and increase from baseline ≥ 10

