6.13. CGM Analyses

The analyses described in this section will be based on the efficacy estimand, including data collected from first dose to last dose of study drug (i.e., open-label Humalog used during the lead-in period or IP used during the treatment period, excluding data (if any) that are collected while patients are temporarily off pump or off study treatment.

In addition, for the FDA submission, the analyses of the multiplicity adjusted objectives on CGM endpoints will also be performed for the ITT estimand. All of the variables will be derived for baseline, Visit 10 (Week 6-8), and Visit 13 (Week 14-16). For baseline, the variables will be derived based upon the data collected during the 2-week open-label Humalog treatment period. For Visit 10, the derivation will be based upon all the data collected during the visit interval of Visit 9, 10, and 11, taking into consideration that some patients may have the sensor inserted before Visit 9 or have the sensor removed after Visit 10.

[Table ITRO 6.5](#) lists all numerical measures for CGM data.

To ensure that the CGM outcome variables are only calculated from CGM session days with sufficient data within the 24-hour, daytime (0600 hours to midnight), or nighttime (midnight to 0600 hours) periods, the following criterion will be used to determine a valid CGM session day to be counted into the calculation for a visit: minimum number of measures per day – at least 70% of the total measures that are supposed to be obtained (i.e., 70% of the 288 measures) for the 24-hour period.

Similarly, for the by-meal outcome variables, the following criteria will be used to determine a valid CGM session day for a visit: minimum number of measures per day – at least 70% of the total measures that are supposed to be obtained. For example, 70% of the 24 measures for the iAUC_{0-2hr} after breakfast.

The definition and derivation of these variables are described in detail in [Appendix 2](#).

Table ITRO 6.5. Outcome Measures of CGM Data

Category	Endpoints	24-Hour	Daytime ^a	Nighttime ^b	By Meal ^c
Efficacy Endpoint: Glucose in the Target Ranges					
	Duration (in minutes) and percentage of time with sensor glucose values within target range 70 to 180 mg/dL [3.9 and 10.0 mmol/L], both inclusive	X	X	X	X
	Duration (in minutes) and percentage of time with sensor glucose values within target range 70 to 140 mg/dL [3.9 and 7.8 mmol/L], both inclusive	X	X	X	X

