The meal time will be collected in the database by eCRF both for the MMTT and non-MMTT meals. The non-MMTT meals include all outpatient meals including morning (breakfast), midday (lunch) and evening (dinner) meals and overall (across the 3 meals). For the non-MMTT meals, only the first meal marker time will be used for each category (breakfast, lunch or dinner). Any data collected after the next meal (regardless of the category of the next meal) will be censored for the analysis with regards to the current meal. No outcome variables will be derived for bedtime meal but its time will be used to censor the data when deriving outcome variables for dinner. Time in ranges by meal will be derived for 0 to 1 hour, 0 to 2 hours, 0 to 3 hours and 0 to 4 hours after the start of each meal while variability by meal will only be derived for 0-4 hours.

All continuous variables will be analyzed using a similar MMRM model as used for the primary endpoint. If the percentage of patients with baseline missing (potentially due to missing meal event markers) is greater than 20% for any meal, a constrained longitudinal data analysis (cLDA) will be performed for all PPG-related CGM endpoints for that meal with treatment, strata (pooled country and patient's personal CGM use during the study), visit, and 2 dummy variables

to indicate treatment effect of LY90014 relative to Humalog at Visit 10 and Visit 13, respectively. An unstructured covariance structure will be used to model the within-patient errors. Significance tests will be based on LS means and Type III tests. SAS PROC MIXED will be used to perform the analysis. If this analysis fails to converge, the same order of the covariance structures will be tested as specified in Section 6.11.1.

Hypoglycemia/hyperglycemia rate per year as measured by CGM data will be analyzed using a negative binomial regression model with treatment as a covariate and an offset defined as the log transformation of days of CGM use/365.25 days. The proportion of patients with at least 1 hypoglycemia/hyperglycemia event as measured by CGM data (incidence) will be analyzed using a logistic regression model with treatment in the model. Similarly, proportion of patients who have achieved the guidance (Battelino 2019) recommended CGM targets of glycemic control (Table ITRO.6.6) during the 14 to 16 weeks of the treatment period will be summarized by treatment and analyzed using the same analysis methods.

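### Non-severe hypoglycaemia and CGM episode rate models leave the lead-in rate and strata unused, a modest precision loss in common categories; separately, the SAP does not settle whether the time-in-range models (H5/H6) include the HbA1c stratum

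*SAP*

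**What the plan says.** **Rate models.** SAP 6.12.3.1 says the number of non-severe diary events "during 0 to 16 weeks (rate) after randomization will be analyzed by using a negative binomial regression model including treatment". Table ITRO 6.3 repeats this for documented, nocturnal, daytime and post-meal events: "Negative binomial regression with treatment and log (exposure/365.25 days) as the offset in the model". For CGM hypo- and hyperglycaemic episodes, SAP 6.13 says the yearly rate "will be analyzed using a negative binomial regression model with treatment as a covariate and an offset" for days of CGM use. Protocol 10.3.4 already has the diary model: the event count "will be analyzed by using a negative binomial regression model including treatment. An offset defined as the log transformation of treatment exposure".

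**What is collected.** Table ITRO 6.2 defines a Visits 2-4 baseline for diary hypoglycaemia. On CGM, SAP 6.13 states: "For baseline, the variables will be derived based upon the data collected during the 2-week open-label Humalog treatment period". On the strata, SAP 6.2 states: "The analysis models will use the stratification factors as collected at randomization in the database as fixed effects".

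**Status.** The rate endpoints are outside the graphical procedure; SAP 6.5 states: "No multiplicity test adjustment will be made for other objectives".

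**H5/H6.** SAP 6.11.2 and 6.13 send time in range to an MMRM described only as similar to the primary one. The primary MMRM (SAP 6.11.1) lists country and personal CGM/FGM use but no HbA1c stratum. Protocol 10.3.1 includes the stratum for variables other than HbA1c, and protocol 10.3.3.2 repeats this for time in range.

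**The concern.** A patient's hypoglycaemia rate in the lead-in may predict the rate on treatment. A model without it leaves between-patient variation in the error and widens the interval for the rate ratio. Hypoglycaemia rates are named secondary objectives, so a tighter interval is useful if it costs little.

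H5 and H6 are different because they are alpha-controlled. Two programmers could fit models with and without the HbA1c stratum and both claim to follow the SAP. The terms of a confirmatory model should be fixed before unblinding and should match the protocol.

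**Working it through.** **Plan's own figure.** The plan states no power or precision for hypoglycaemia rates, CGM episode rates or H5/H6. Its only power statement is for HbA1c, and it reproduces:
- SE = 0.88 × √(2/184) = 0.0917.
- Margin 0.4: Φ(0.4/0.0917 − 1.96) = Φ(2.40) = 99.2%.
- Margin 0.3: Φ(0.3/0.0917 − 1.96) = Φ(1.31) = 90.5%.
- 368/(1 − 0.12) = 418.2, against about 420 planned.

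None of this is in dispute.

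**Part 1: models compared.**
- Plan: log E(count) = α + β·treatment + log(exposure/365.25).
- Adjusted: the same plus γ·log((lead-in count + 0.5)/lead-in exposure), with or without strata.

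*From the documents:* 420 randomised 1:1, 12% dropout, 2-week lead-in (14 days), 16-week treatment (112 days), stratified randomisation. *Assumed:* event rate, frailty variance 0.5-1.0, and lead-in/treatment correlation of the latent rates 0.3-0.8.

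The event rate matters because the expected lead-in count is rate × 14/365.25: about 3.1 at 80 per year, 0.77 at 20, 0.19 at 5 and 0.08 at 2.

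Simulated SE of β, lead-in model relative to treatment-only (no treatment effect, 450 replicates per cell):

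| Rate/year | Variance | Corr. 0.6 | Corr. 0.8 |
|---|---|---|---|
| 5 | 0.5 | 0.994 | 0.990 |
| 5 | 1.0 | 0.986 | 0.976 |
| 20 | 0.5 | 0.968 | 0.945 |
| 20 | 1.0 | 0.952 | 0.913 |
| 40 | 0.5 | 0.945 | 0.903 |
| 40 | 1.0 | 0.926 | 0.862 |
| 80 | 0.5 | 0.915 | 0.846 |
| 80 | 1.0 | 0.907 | 0.814 |

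- **Lower correlations**, 20-80 per year: the SE falls 0.6-2.1% at 0.3 and 1.2-3.7% at 0.4.
- **Rare events:** at 2 per year about 93% of patients have a lead-in count of zero, and the SE hardly moves.
- **Realised SD**, mean ratio over 20-80 per year: 0.936 at correlation 0.6 and 0.889 at 0.8. In patients, 1/0.936² − 1 = 14% and 1/0.889² − 1 = 27%.
- **CGM episodes**, 50-300 per patient-year: SE ratio 0.875-0.959 at 0.6 and 0.745-0.923 at 0.8.
- **Second simulation**, differently built (strata and lead-in count, correlation 0.5 and 0.8): SE ratio 0.96-0.98 at 5 per year, 0.87-0.95 at 30 and 0.81-0.93 at 80.
- **Strata alone**, stratum rate ratio 1.25, 1.5 and 2.0: the model SE falls 1-2%, 3-8% and 8-26%. The realised SD falls only 0.4%, 2.3% and 5.4%, because randomisation already balances the strata. The real gain is mainly from the lead-in rate.
- **Null rejection**, treatment-only to lead-in plus two strata: diary 5.3% to 5.7% (robust SE 5.2% to 5.5%); CGM 4.3% to 5.6% (robust 4.3% to 5.4%).
- **Missing baselines:** dropping 10% or 20% of patients multiplies the SE by 1/√0.9 = 1.05 or 1/√0.8 = 1.12.

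**Part 2: H5/H6, passages side by side.**
- For inclusion: protocol 10.3.1 and 10.3.3.2. SAP 6.2 also makes strata the default and removes the HbA1c stratum only for the primary HbA1c analysis.
- For omission: SAP 6.11.2 writes the stratum out for H2/H3 but not for H5/H6. The one CGM model whose terms SAP 6.13 lists (the by-meal fallback) has pooled country and CGM use only.
- Mixed: SAP 6.11.4 includes the stratum for time in hypo- and hyperglycaemia, while 6.13 sends all continuous CGM variables to the similar model.

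If the stratum has partial R² given baseline, omitting it multiplies the SE by 1/√(1 − R²). That is +0.50% at 0.01, +1.53% at 0.03 and +2.60% at 0.05. Under stratified randomisation the true two-sided size becomes 4.89%, 4.66% and 4.43%. A direct simulation with baseline time in range in the model gave an SE change of 0.3-1.2%.

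**The case against.** **The SAP follows the protocol.** The treatment-only diary model is in both documents, written out in text and table. An unadjusted negative binomial comparison is valid in a randomised trial. A reader might infer that the models contradict SAP 6.2, but a model written out in full governs over a general sentence. Other safety models also leave out strata, such as the vital-signs "MMRM model with treatment, baseline value of the response variable, visit, and visit by treatment interaction as fixed factors". This stands: 6.2 should state its exemptions, but there is no clear contradiction. The same vital-signs model does, however, adjust for baseline value, so it is no precedent for ignoring the lead-in rate.

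**The gain could be near zero.** Some patients change insulin at Visit 2, users of the suspend-before-low feature must stop it, and settings are titrated for 16 weeks. The correlation could be low, so the range must include 0.3-0.4. This stands.

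**Early post-meal events gain least.** Protocol 5.5 names them as a possible added risk, and a reader might use that to justify adjustment. They and events below 54 mg/dL are subsets of all documented events, hence rarer, and there the lead-in count carries little information. That justification fails.

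**Adjustment has costs.** Null rejection rises slightly. SAP 6.13 provides for more than 20% missing baselines in by-meal CGM endpoints, and a complete-case covariate model would lose those patients. Both stand and limit the fix.

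**H5/H6 may already be right.** A reader might conclude that the SAP drops the stratum. The text does not establish that: similar is loose, protocol 10.3.3.2 uses the same word while adding the stratum, and SAP 6.2 does not exempt time in range. The by-meal fallback is not the H5/H6 model. What remains is an ambiguity.

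**Conclusion.** **Part 1** is a worthwhile, low-cost improvement in precision. There is no bias or type I error problem in the planned models, and no alpha-controlled conclusion depends on them. For common diary categories (20-80 per patient-year) the SE of the log rate ratio would fall about 1-4% at a lead-in correlation of 0.3-0.4, 3-9% at 0.6 and 5-19% at 0.8. At 5 per year or fewer it would fall 0-2.4%. For CGM episodes at 50-300 per patient-year it would fall 4-13% at 0.6 and 8-26% at 0.8. Every figure rests on assumed rates, dispersion and correlation, since the documents give none. The case is for all documented events and for 24-hour and daytime CGM episodes.

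**Part 2** is a minor reconciliation. The SAP does not settle whether the H5/H6 models carry the HbA1c stratum that the protocol requires. The SE differs by about 0.3-2.6%, and omission would make the test slightly conservative. The reason to act is that these are confirmatory hypotheses.

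**What to change.** 1. **Common categories** (all documented diary events; 24-hour and daytime CGM episodes): add log((lead-in count + 0.5)/lead-in exposure), HbA1c stratum and personal CGM/FGM use to the negative binomial model, and report robust SEs. Keep treatment-only as the sensitivity analysis.
2. **Rare categories and by-meal CGM episodes:** keep treatment-only as the main model.
3. **Missing lead-in data:** retain these patients by a stated rule, for example mean imputation of the covariate with a missing indicator.
4. **Country:** leave it out unless counts allow. In simulation, seven country terms raised the realised SD by 0.3-1.0% while the model SE fell about 1%, and null rejection went from 5.2% to 5.6%.
5. **SAP 6.2:** state which event models are exempt from stratum adjustment (severe hypoglycaemia, logistic incidence).
6. **SAP 6.11.2 and 6.13:** list the H5/H6 MMRM terms as treatment, pooled country, HbA1c stratum, CGM/FGM use, baseline, visit and treatment-by-visit. Align 6.13 with 6.11.4 for time in hypo- and hyperglycaemia.

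The cost is SAP text and some programming; all covariates are already collected. SAP 6.1 allows a method change to be recorded and justified in the SAP unless it alters a principal feature of the protocol. The downside is little gain in sparse categories and the slight rise in model-based null rejection shown above.
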